8.0 STATISTICAL ANALYSIS PLAN

This section outlines the statistical analysis strategy and procedures for the study. If, after the study has begun, but prior to unblinding, changes are made to the primary and/or key secondary hypothesis, or the statistical methods related to those hypotheses, then the protocol will be amended (consistent with ICH Guideline E-9). Changes to exploratory or other non- confirmatory analyses made after the protocol has been finalized, but prior to unblinding, will be documented in a supplemental Statistical Analysis Plan (sSAP) and referenced in the Clinical Study Report (CSR) for the study. Post hoc exploratory analyses will be clearly identified in the CSR.

8.1 Statistical Analysis Plan Summary

Key elements of the statistical analysis plan are summarized below; the comprehensive plan is provided in Sections 8.2 to 8.12.

Study Design Overview	Omarigliptin Phase IV Study -Omarigliptin Add-on to Insulin in Japanese T2DM
Treatment Assignment	Subjects will be randomized to omarigliptin and placebo in a 2:1 ratio. The study will be conducted as a double-blind study up to Week 16 and following extension part up to Week 52 will be conducted as an open-label study.
Analysis Populations	Efficacy Full Analysis Set (FAS) population, defined as all randomized subjects who: 
 • received at least one dose of treatment period study medication • have at least one measurement of the outcome variable (baseline or post-randomization) Safety All Subject as Treated (ASaT) population, defined as all randomized subjects who received at least one dose of treatment period study medication.
Primary Endpoint	Change from baseline in HbA1c at Week 16
Secondary Endpoint	Change from baseline in FPG at Week 16
Statistical Methods for Key Efficacy Analyses	Change from baseline in HbA1c at Week 16 will be analyzed using a constrained longitudinal data analysis (cLDA) model proposed by Liang and Zeger [12]. The model will include terms for treatment, prior AHA therapy status (yes/no), time and the interaction of time by treatment, time by prior AHA therapy status and time by treatment by prior AHA status. The primary hypothesis which is the superiority of omarigliptin to placebo, will be evaluated by using the cLDA model.
Statistical Methods for Key Safety Analyses	Safety will be assessed following a tiered-approach by clinical review of all relevant parameters including AEs, PDLCs, laboratory tests, vital signs, body weight and ECG. AEs of symptomatic hypoglycemia will be pre-specified as Tier 1 events. The percentage of subjects experiencing Tier 1 events will be analyzed using the Miettinen and Nurminen method [13]. P-Values for treatment comparisons and 95% confidence intervals (CIs) for treatment differences will be provided.
Interim Analyses	No interim analysis is planned.
Multiplicity	Given a single primary hypothesis, no multiplicity adjustment is required.
Sample Size and Power	A sample size of 180 subjects in a 2:1 ratio (i.e., 120 and 60 subjects for omarigliptin and placebo, respectively) will provide 97% power to detect a treatment difference of 0.50% in HbA1c reduction from baseline at Week 16 ($\alpha=0.05$, two-sided test) based on the conditional standard deviation of 0.82% and the correlation matrix and subject attrition assumptions specified in Section 8.9. The half-width of the 95% CI is expected to be 0.26%. In addition, the sample size is expected to provide 100 or more subjects exposed for one year (omarigliptin group only), assuming 15% discontinuation rate for 52 weeks.

8.2 Responsibility for Analyses/In-House Blinding

The statistical analysis of the data obtained from this study will be the responsibility of the SPONSOR.

This study will be conducted as a double-blind study for first 16-weeks [Phase A (double-blind period)] under in-house blinding procedures with following 36-weeks extension part [Phase B (Open-label period)], i.e. total of 52-weeks study. With regard to Week 16, the official, final database for Week 16 will not be unblinded until medical/scientific review has been performed, protocol violators have been identified, and data have been declared final and complete. With regard to Week 52, the official, final database will not be frozen until medical/scientific review has been performed and data have been declared final and complete. The Clinical Biostatistics department in Merck will generate the randomized allocation schedule for study treatment assignment.

8.3 Hypotheses/ Estimation

Objectives and hypotheses of the study are stated in Section 3.0.

8.4 Analysis Endpoints

Efficacy and safety endpoints that will be evaluated for within- and/or between-treatment differences are listed below.

The baseline value will be defined as the Visit 4/Day 1/Randomization measurement. If this measurement is not available, the Visit 3/Week -2 measurement will be used as the baseline value. If neither measurement is available, the baseline value will be treated as missing. The primary time point is Week 16.

8.4.1 Efficacy Endpoints

The efficacy measurements and time points at which they are measured are provided in Section 6.0 (the Trial Flow Chart).

The primary efficacy endpoint in the study is the change from baseline in HbA1c at Week 16.

The secondary efficacy endpoints in the study are the change from baseline in Fasting Plasma Glucose (FPG) and 1,5-anhydroglucitol (1,5-AG) at Week 16, and the percentages of subjects at HbA1c goals (<7.0% and <6.5%) at Week 16.

The other secondary efficacy endpoints in the study are the change from baseline in HbA1c and FPG at Week 52 and the percentages of subjects at HbA1c goals (<7.0% and <6.5%) at Week 52.

The insulin dose and percentages of subjects with up-titration and down-titration of insulin dose at Week 16 and Week 52 are other efficacy endpoints.

In describing the efficacy variables of interest below, the description is restricted to the primary time point of interest (Week 16). However, many variables are measured at additional time points, as indicated in the Trial Flow Chart (Section 6.0), and will be summarized at other time points.

Table 9 Efficacy Endpoints

Primary Endpoint Change from baseline in HbA1c at Week 16
Secondary Endpoint Change from baseline in FPG at Week 16 Percentages of subjects at HbA1c goals (<7.0% and <6.5%) at Week 16
Change from baseline in 1,5-AG at Week 16
Change from baseline in HbA1c at Week 52
Change from baseline in FPG at Week 52
Percentages of subjects at HbA1c goals (<7.0% and <6.5%) at Week 52

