Subjects on pre-mixed/fixed ratio combination (content percentage of rapid-acting or ultra rapid-acting insulin is lower than or equal to 30%), intermediate or long-acting insulin monotherapy are eligible to participate.

Consistent dosage and administration schedule of insulin will be used during the trial. In Phase A (double-blind period), the dosage must be kept at the dosage used at Visit 1/Screening, unless the subject meets hypoglycemia criteria for down-titration, or glycemic rescue criteria for up-titration of insulin. During Phase B (open-label period), the investigator can modify dose of insulin as clinically required for appropriate glycemic control, in addition to insulin adjustment based on the protocol-specified rescue/hypoglycemia criteria.

Specific procedures to be performed during the trial, as well as their prescribed times and associated visit windows, are outlined in the Trial Flow Chart - Section 6.0. Details of each procedure are provided in Section 7.0 – Trial Procedures.

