5.6 Rescue Medications & Supportive Care

5.6.1 Rescue treatment (up-titration of insulin)

The subject who meets the following glycemic rescue criteria in [Table 4](#) should initiate rescue therapy with up-titration of the insulin that they are receiving during the trial (continuing from Visit 1/Screening).

Table 4 Rescue criteria

Application Timing	Criteria	Administration Timing
After Visit 4/Day 1/Randomization to Visit 10/Week 24	FPG (as reported by the central lab) is repeatedly * confirmed >240 mg/dL two times	At the next scheduled or unscheduled Visit (= Rescue Visit)
After Visit 10/Week 24	FPG (as reported by the central lab) is repeatedly * confirmed >200 mg/dL two times	

* Repeatedly at the scheduled visit (or at unscheduled visit as needed).
After initiation of rescue therapy, insulin can be adjusted by judgment of the investigator even if the FPG does not show "repeatedly" the above criteria.

Subjects that meet rescue criteria will have their insulin dose adjusted as determined clinically appropriate by the investigator to manage glycemic control. The maximum dosage of insulin should follow the maximal approved dose based on its package insert.

During Phase A, up-titration of insulin relative to the dose at Visit 4/Day 1/Randomization may be performed only if the subject has glucose measurements meeting rescue criteria, during Phase B, up-titration will be determined by investigator's assessment of subject's need for glycemic control.

Subjects will continue on study medication after initiation of rescue therapy or down-titration of insulin until completion unless they meet discontinuation criteria (See Section 5.8).

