To avoid the confounding influence of rescue therapy on efficacy comparisons at Week 16, efficacy analyses in the FAS and PP populations will treat data as missing after the initiation of rescue therapy. Outlines on the approach to handling missing data are provided in Section 8.6, Statistical Methods. Sensitivity analysis to assess the impact of missing data will be described in sSAP.

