Change from baseline in FPG at Week 52	P	Summary Statistics	FAS	N/A
Percentages of subjects at HbA1c goals (<7.0% and <6.5%) at Week 52	P	Summary Statistics	FAS	N/A
P=Primary; S=Secondary.				
§ Sensitivity analyses will be performed to assess the impact of missing data. Details will be provided in the sSAP.				

For long-term efficacy data up to Week 52, the mean change and the 95% confidence intervals will be calculated by treatment groups of double-blind period to assess the long-term efficacy of omarigliptin. The mean change will be computed relative to baseline (Visit 4/Day 1/Randomization). Between-groups comparisons and/or estimation of between-group difference will not be performed.

For the HbA1c goals of <7.0% and <6.5% at Week 52, the percentage of individuals and the 95% confidence intervals will be calculated using Wilson score method [16] by treatment groups of double-blind period.

For long-term efficacy analyses, all data will be included in the analysis regardless of initiating the rescue therapy since insulin dose during extension period are allowed to down or up –titrate if clinically required.

The summary statistics for the insulin dose, percentages of subjects with up-titration and down-titration of insulin dose will be generated by treatment group of double-blind period at Week 16 and Week 52.

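### The post-rescue missing-data rule, as written, removes rescued subjects' insulin doses from the Week 16 insulin-dose and titration endpoints

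*Combined protocol and SAP*

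**What the plan says.** Section 8.4.1 classes the insulin measures as efficacy endpoints: "The insulin dose and percentages of subjects with up-titration and down-titration of insulin dose at Week 16 and Week 52 are other efficacy endpoints". They do not appear in Table 9 or Table 10.

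Section 8.5.1 sets the data rule: "efficacy analyses in the FAS and PP populations will treat data as missing after the initiation of rescue therapy". Section 8.6.1 repeats it. Neither place exempts the insulin endpoints.

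Section 5.6.1 defines rescue as an insulin increase. A subject who meets the criteria "should initiate rescue therapy with up-titration of the insulin that they are receiving during the trial". It also closes every other route upward during the double-blind period: "up-titration of insulin relative to the dose at Visit 4/Day 1/Randomization may be performed only if the subject has glucose measurements meeting rescue criteria". Section 2.1 agrees that the Phase A dose stays fixed "unless the subject meets hypoglycemia criteria for down-titration, or glycemic rescue criteria for up-titration of insulin".

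Section 8.6.1 then asks for summary statistics of insulin dose and of the two titration percentages, which "will be generated by treatment group of double-blind period at Week 16 and Week 52". It names no population and no rescue rule for them. Just before that, it includes all data regardless of rescue, but for long-term efficacy analyses, and the reason it gives is that insulin may be titrated in the extension period.

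**The concern.** The rule was written for HbA1c and FPG, where insulin given as rescue would mask the drug effect. For the insulin endpoints, the rescue increase is itself part of what is being measured. A rule that deletes data after rescue therefore deletes the doses that these summaries are meant to describe, while doses reduced for hypoglycemia stay in.

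In a placebo-controlled trial of a drug added to insulin, a need for more insulin is a direct sign of inadequate glycemic control. If more placebo than omarigliptin subjects need rescue, the Week 16 insulin table would hide some or all of that difference. Two programmers working from the same text could also produce different tables.

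**Working it through.** **1. The plan's own figures.** The documents state no expected rescue or up-titration percentage, so there is none to reproduce. The design inputs in Section 8.9 do reproduce. The stated correlation matrix and attrition give an information fraction of 0.9778, and 0.9778 × 180 = 176.0 (stated: 176). With 2:1 allocation of 176, SD 0.82 and a difference of 0.5, power is 96.8% (stated: 97%). None of this depends on the insulin endpoints.

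**2. The chain of rules.**
- Insulin dose and titration at Week 16 are efficacy endpoints (8.4.1).
- Efficacy data after the start of rescue are missing (8.5.1, 8.6.1).
- In Phase A, a dose above the Visit 4 dose is permitted only as rescue (5.6.1).
- So every permitted Week 16 dose above the Visit 4 dose is a post-rescue value and is missing. Later adjustments, which 5.6.1 allows once rescue has begun, are missing too.
- Permitted reductions in subjects without rescue stay in.

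**3. Percentage up-titrated.** Section 8.9 puts cumulative attrition at Week 16 at 5%, and this includes HbA1c data lost to rescue: 0.05 × 180 = 9 subjects. The table assumes that all 9 were rescued, that no other data are missing, and that there are no protocol deviations. The splits between arms are assumptions.

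| Assumed rescue, omarigliptin / placebo | Subjects rescued | Status at Week 16, rule applied | Event up to Week 16, initiating increase counted |
|---|---|---|---|
| 5% / 5% | 6/120, 3/60 | 0/114, 0/57 | 5%, 5% |
| 2.5% / 10% | 3/120, 6/60 | 0/117, 0/54 | 2.5%, 10% |

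The plan does not say which of the two readings it means.

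**4. Mean change in dose from Visit 4.** Let r be the share rescued, u their mean increase, and m the mean change in everyone else.
- All data: r × u + (1 − r) × m.
- With the rule: m.
- Understatement: r × (u − m).

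With r = 0.05, m = 0 and u assumed to be 4 to 10 units, this is 0.05 × 4 = 0.2 to 0.05 × 10 = 0.5 units. Permitted reductions make m slightly negative, which widens the gap a little. If less of the 5% is rescue, the gap shrinks in proportion.

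The error falls mainly on the arm with more rescue. In the 2.5% / 10% split it is 0.025 × 4 = 0.1 to 0.025 × 10 = 0.25 units on omarigliptin, and 0.10 × 4 = 0.4 to 0.10 × 10 = 1.0 units on placebo. Over all 180 subjects it is still 0.2 to 0.5.

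**5. Mean dose itself.** Entry doses run from 8 to 40 units/day (5.1.2). Removing a rescued subject also removes that subject's starting dose. If someone who went from 10 to 14 units is dropped from an arm averaging 20, the arm mean rises. The direction of error is therefore fixed for mean change from Visit 4, but not for mean dose.

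**The case against.** The strongest reply is that the rule was never meant for this table. Its stated purpose is to protect Week 16 efficacy comparisons from confounding by rescue, and rescue cannot confound a count of rescue. The insulin summaries are descriptive, untested, tied to no named population, and absent from Tables 9 and 10. The sentence that requests them follows directly after the all-data statement and covers Week 16 and Week 52 together. This makes an intended exemption plausible, but no text states one. The rule's operative wording covers efficacy analyses, 8.4.1 places these endpoints there, and the reason given for the exemption (titration in the extension period) does not reach Phase A. For double-blind safety data, Section 8.6.2 spells out one approach without and one with post-rescue data. Nothing similar is said for insulin.

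The second reply is that the increase that starts rescue is arguably the cut-off event and not data after it. This stands. A reader might infer that permitted up-titration must show as 0% in both arms whatever the true rates. The documents support that only if the endpoint is dose status at Week 16, and they leave the term undefined. The phrase placing the endpoint at Week 16 leans towards status but does not settle it. Rescue begun at the Week 16 visit itself, and a dose partly restored after a reduction, are further unsettled cases.

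A reader might also infer that mean insulin dose could only stay level or fall. Step 5 of the working shows that this does not follow.

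Finally, insulin dose is in no objective or hypothesis, and Section 8.0 sends changes to non-confirmatory analyses to the supplemental SAP, which is not among the documents. That limits the importance of the point. It does not remove the conflict in the text.

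**Conclusion.** The plan is wrong as written, with minor impact. Applied literally, the rule excludes rescued subjects' Week 16 insulin doses, and mean change from Visit 4 keeps permitted decreases while losing permitted increases. This holds on either reading of up-titration. The 0% result in both arms holds only on the status reading.

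The size depends on a rescue rate that the documents do not give. The figure of at most about 0.2 to 0.5 units in mean change, over both arms together, rests on three assumptions: all of the planned 5% attrition is rescue, increases are 4 to 10 units, and other subjects' mean change is near zero. That is small against entry doses of 8 to 40 units/day, though it could fall mostly on one arm.

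The primary HbA1c analysis and its power are untouched. Week 52 is covered by the long-term exemption.

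**What to change.** In Sections 8.5.1 and 8.6.1, or in the supplemental SAP before unblinding:

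- State that the post-rescue missing-data rule does not apply to the Week 16 summaries of insulin dose and titration.
- Count a subject as up-titrated or down-titrated if the dose was above or below the Visit 4/Day 1 dose at any time up to Week 16, rescue included, with all treated subjects as the denominator.
- Summarise insulin dose, and its change from Visit 4, in subjects with an observed Week 16 dose, regardless of rescue. All treated subjects cannot be the denominator here, because those who have left have no Week 16 dose to average.

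The cost is a few sentences. The plan already requires insulin dose and titration to be summarised, so no new data are needed, and no treatment rule changes.

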8.4.2 Safety Endpoints

The primary safety endpoint (i.e. Tier 1 safety endpoint) is the percentage of subjects experiencing one or more adverse events of symptomatic hypoglycemia, regardless of glucose value.

Other safety endpoints include adverse events, percentages of subjects meeting predefined limits of change in laboratory parameters (including blood chemistry and hematology), change (or percent change) from baseline at Week 16 and Week 52 in laboratory parameters, ECG, vital signs and body weight, and the numbers and percentages of subjects experiencing one or more of each the following:

- Adverse events of hypoglycemia (symptomatic or asymptomatic)
- Documented symptomatic hypoglycemia: An episode with clinical symptoms attributed to hypoglycemia with a documented glucose level of ≤ 70 mg/dL.
- Severe hypoglycemia, defined as adverse events of symptomatic hypoglycemia that required assistance, either medical or non-medical, regardless of whether such assistance was obtained. These events will be further sub-classified as:
 - Those that required medical assistance. Adverse events of symptomatic hypoglycemia that included a markedly depressed level of consciousness, loss of consciousness, or seizure will be classified as having required medical assistance, whether or not medical assistance was obtained.
 - Those that did not require medical assistance. (i.e., those episodes that required non-medical assistance to treat).
- Asymptomatic hypoglycemia: An episode with a documented glucose level of ≤ 70 mg/dL but without clinical symptoms attributed to hypoglycemia.

8.5 Analysis Populations

8.5.1 Efficacy Analysis Populations

The Full Analysis Set (FAS) population will serve as the primary population for the analysis of efficacy endpoints in this study. The FAS population consists of all randomized subjects who:

- receive at least one dose of study treatment.
- have at least one measurement (baseline or post-randomization).

A secondary population for analyzing efficacy endpoints will be the Per-Protocol (PP) population. The PP population consists of all randomized subjects who have a baseline (Visit 4/Day 1/Randomization) measurement and a measurement at Week 16, without the following protocol violations.

Protocol violations are not just a repetition of the exclusion and inclusion criteria in the protocol, but a clinical assessment of deviations from the protocol-specified criteria that will either affect or confound the measures of efficacy. Subjects meeting any of the following criteria will be excluded from the per-protocol population (at all time points).

- Study drug compliance <75%, with compliance based on prime therapy records using the formula provided in Section 8.11.
- Use of prohibited medications, based on the list of prohibited medications in Section 5.5, as follows:
 - Prohibited anti-hyperglycemic medications after randomization (Visit 4/Day 1/Randomization) for a total of ≥ 14 days or ≥ 7 consecutive days.
 - Pharmacologic doses of corticosteroid use ≥ 2 consecutive weeks during the study period of interest.
- Incorrect double-blind study medication for a total of ≥ 14 days (two times) during the study period of interest.

The final determination on protocol violations, and thereby the composition of the PP population, will be made prior to unblinding of the database for week 16 and will be documented in a separate memo.

Any substantial differences between conclusions based on the FAS population and the PP population will be investigated. The number of subjects included in the FAS and PP populations may vary across endpoints due to the degree of missing data for each endpoint.

Subjects will be included in the treatment group to which they are randomized for all analyses of efficacy data.

To avoid the confounding influence of rescue therapy on efficacy comparisons at Week 16, efficacy analyses in the FAS and PP populations will treat data as missing after the initiation of rescue therapy. Outlines on the approach to handling missing data are provided in Section 8.6, Statistical Methods. Sensitivity analysis to assess the impact of missing data will be described in sSAP.

8.5.2 Safety Analysis Populations

The All-Subjects-as-Treated (ASaT) population will be used for the analysis of safety data in this study. The ASaT population consists of all randomized subjects who received at least one dose of study treatment. Subjects will be included in the treatment group corresponding to the study treatment they actually received for the analysis of safety data using the ASaT population. This will be the treatment group to which they are randomized for all subjects except for those who take incorrect study treatment for the entire treatment period. Such subjects will be included in the treatment group corresponding to the study treatment actually received.

At least one laboratory or vital sign measurement obtained subsequent to at least one dose of study treatment is required for inclusion in the analysis of each specific parameter. To assess change (or percent change) from baseline, a baseline measurement is also required.

All safety endpoints analyses will be based on the observed data (i.e., with no imputation of missing data).

